4.1 Study Design

This is a post-market, real world, prospective, multicenter study evaluating the use of the Indigo[®] Aspiration System with the CAT RX Aspiration Catheter (and Indigo SeparatorTM 4, if needed) as a frontline adjunctive treatment to standard of care PCI. Patients will be enrolled who meet the inclusion and none of the exclusion criteria, who (or Legally

Authorized Representative (LAR)) consent to participate, and in whom the study device has been inserted.

4.2 Study Objectives/Endpoints

4.2.1 Primary Endpoints

Composite of cardiovascular (CV) death, recurrent MI, cardiogenic shock, or new or worsening NYHA Class IV heart failure within 30 days.

4.2.2 Secondary Endpoints

Performance:

- 1. Final TIMI Flow Grade
- 2. Final TIMI Thrombus Grade
- 3. Myocardial Blush Grade
- 4. Distal Embolization Rate
- 5. Stent thrombosis at 180 days

Safety:

- 1. Stroke within 30 days
- 2. Major bleeding within 30 days
- 3. All-cause mortality within 180 days
- 4. Cardiovascular (CV) death within 180 days
- 5. Recurrent MI within 180 days
- 6. Cardiogenic shock within 180 days
- 7. Class IV heart failure within 180 days
- 8. Incidence of device related SAE(s)

5. Study Population

5.1 Inclusion Criteria

- 1. Patient age \geq 18 years
- 2. Patient presents to treating facility within 12 hours of symptom onset
- 3. High thrombus burden at coronary angiography, defined as TIMI thrombus grade 4 or 5 by physician visual estimate after the guidewire crosses the target lesion
- 4. Frontline treatment with the Indigo® Aspiration System using the CAT RX Aspiration Catheter, prior to standard of care PCI
- 5. Target lesion is located in a native coronary artery
- 6. Informed consent is obtained from either patient or legally authorized representative (LAR)

5.2 Exclusion Criteria

- 1. New onset of stroke symptoms and NIHSS > 2, prior to index procedure
- 2. Treatment with fibrinolytic therapy for index coronary vessel occlusion
- 3. Life expectancy less than 6 months due to any comorbidities
- 4. Patient is unwilling or unable to comply with protocol follow up schedule and/or based on the Investigator's judgement the patient is not a good study candidate
- 5. Participation in another investigational drug or device study that may confound the results of this study. Studies requiring extended follow-up for products that were investigational but have since become commercially available are not considered investigational studies
- 6. Patient is pregnant

6. Study Procedures

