6.4 Screening & Enrollment

Enrollment process:

- 1. Confirm that the subject meets all inclusion and no exclusion criteria.
- 2. Obtain informed consent from the patient or LAR.
- 3. A subject will be considered enrolled when all eligibility criteria are met, the subject or LAR has given informed consent and the Indigo CAT RX Aspiration Catheter has been inserted into the subject's body. Subjects who have had a procedure (using the Indigo® Aspiration System with the CAT RX Aspiration Catheter as a frontline adjunctive to PCI) prior to signing informed consent may be consented up to 2 calendar days post-procedure, but prior to initial discharge, and enrolled into the study.
 - a. The point of enrollment is defined as the date of informed consent or introduction of the CAT RX Aspiration Catheter, whichever occurs later.
 - b. All follow-up visits will be conducted based on date of procedure, regardless of enrollment date.

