10.5.2 Screen Failure

Screen failure patient are all patients considered for participation in the study, who failed to meet inclusion criteria or met exclusion criteria. Patients can be screen failed based on general or imaging criteria. These patients may or may not have signed an informed consent form.

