New or worsening NYHA Class IV heart failure: defined heart failure symptoms at rest and a physician decision to treat HF with IV diuretic, inotropic agent or vasodilator plus at least one of the following: 1) presence of pulmonary edema or pulmonary vascular congestion on chest radiograph thought to be due to HF; 2) rales reaching above the lower 1/3 of the lung fields thought to be due to HF; or 3) PCWP or LVEDP \geq 18 mm Hg.

No reflow: defined as an acute reduction in coronary flow (TIMI grade 0-1) in the absence of dissection, thrombus, spasm or high-grade residual stenosis at the original target lesion.

Recurrent Ischemia: Recurrent chest pain (with documented ST depression > 1mm in at least 2 contiguous leads on transient ST elevation) lasting more than 5 minutes and leading to additional intervention such as thrombolytic therapy for threatened MI, cardiac catheterization leading to repeat intervention, or insertion of intra-aortic balloon pump or urgent revascularization (UR) by midnight of next calendar day following the initial symptoms.

Stent thrombosis: (Categorized by Timing & Level of Certainty)

a. Timing

- i. Acute Stent Thrombosis: 0 to 24 hours after stent implantation
- ii. Subacute Stent Thrombosis: > 24 hours to 30 days after stent implantation
- iii. Late Stent Thrombosis: >30 days to 1 year after stent implantation

iv. Very Late Stent Thrombosis: >1 year after stent implantation

b. Level of Certainty

i. Definite Stent Thrombosis:

Angiographic confirmation of stent thrombosis: (incidental angiographic documentation of stent occlusion in the absence of clinical signs or symptoms is not considered a confirmed stent thrombosis).

The presence of an intracoronary thrombus that originates in the stent or in the segment 5mm proximal or distal to the stent and presence of at least 1 of the following criteria within a 48-hour time window:

- 1. Acute onset of ischemic symptoms at rest
- 2. New ischemic ECG changes that suggest acute ischemia
- 3. Typical rise and fall in cardiac biomarkers
- 4. Nonocclusive thrombus:

Intracoronary thrombus is defined as a (spheric, ovoid, or irregular) noncalcified filling defect or lucency surrounded by contrast material (on 3 sides or within a coronary stenosis) seen in multiple projections, or persistence of contrast material within the lumen, or a visible embolization of intraluminal material downstream.

5. Occlusive thrombus:

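### Exclusion 2 and the judgement limb of exclusion 4 have no time anchor, yet treated patients may be enrolled up to 2 calendar days later, so those with early events can be screened out of the ITT sample

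*Combined protocol and SAP*

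**What the plan says.** Protocol section 5.2 (repeated in the synopsis) gives exclusion 1 a time limit: "New onset of stroke symptoms and NIHSS > 2, prior to index procedure". Exclusion 2 has none: "Treatment with fibrinolytic therapy for index coronary vessel occlusion". Nor does exclusion 4, whose second limb applies when "based on the Investigator's judgement the patient is not a good study candidate".

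Section 6.4 says that patients already treated frontline with the CAT RX catheter "may be consented up to 2 calendar days post-procedure, but prior to initial discharge, and enrolled into the study". It also sets the condition for entry: "A subject will be considered enrolled when all eligibility criteria are met", with consent given and the catheter inserted. The enrolment date is the later of consent and catheter introduction. Consent is itself inclusion criterion 6.

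Section 10.5.2 classes as screen failures those "who failed to meet inclusion criteria or met exclusion criteria". Section 10.6.1 and SAP section 6 limit the ITT sample to enrolled subjects. Section 6.1 requires a screening log with reasons for exclusion.

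In Table 2, eligibility confirmation is marked at baseline and at the procedure (Day 0). The late-consent footnote extends consent only.

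**The concern.** For a late-consented patient, the set of eligibility criteria can be completed only after the procedural result is known. Early primary events may be known by then too. Section 16.2 defines cardiogenic shock on about 1 hour of hypotension or pressor support, and PCI-related MI within 48 hours of the procedure. Both fit inside the consent window.

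No sentence tells the site to ignore post-insertion information when applying exclusions 2 and 4. A treated patient who did badly can be judged a poor candidate, or be held to meet exclusion 2 because of a fibrinolytic given after aspiration. That patient becomes a screen failure and drops out of both numerator and denominator.

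The study has one arm and is judged against a fixed 16% limit, so no comparator shares the bias. The sensitivity analyses in SAP section 10 cover enrolled subjects with a missing 30-day outcome, not patients who never entered. The log is not required to show whether the reason arose before or after insertion, so the loss could not be measured afterwards.

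**Working it through.** **Inputs.** Protocol sections 10.2 and 10.8 and SAP sections 2 and 7.1 give an assumed rate of 6.1% (22/360), a 16% limit, one-sided alpha 0.025, 360 evaluable subjects and 10% attrition. The share of event patients screened out after treatment, f, is not in the documents and is assumed.

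**The plan's own figures.** 360/(1 − 0.10) = 400, as stated. With an exact one-sample binomial test at n = 360 and a limit of 16%, success needs at most 43 events (43/360 = 11.9%). The exact upper limit is 15.75% at 43 events and 16.06% at 44. The actual one-sided error is 0.0185, and power at a true rate of 6.1% is 0.99999. The stated 99% power is met.

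**Effect of selective screening.** Let p be the 30-day rate in all device-treated patients. If a share f of event patients is screened out, non-event patients are unaffected and places are refilled to 360, the rate among those enrolled is

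q = p(1 − f)/(1 − pf),

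and the chance of success is P(X ≤ 43), with X binomial(360, q).

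True rate 16% (the null boundary):

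| f (assumed) | q | Chance of wrongly meeting the endpoint |
|---|---|---|
| 0 | 16.0% | 1.9% |
| 5% | 0.152/0.992 = 15.3% | 4.1% |
| 10% | 0.144/0.984 = 14.6% | 8.3% |
| 20% | 0.128/0.968 = 13.2% | 26.5% |

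The expected number of patients removed per 360 enrolled is 360 × pf/(1 − pf): 360 × 0.008/0.992 = 2.9, 360 × 0.016/0.984 = 5.9 and 360 × 0.032/0.968 = 11.9 for f = 5%, 10% and 20%.

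True rate 6.1% (the planning value):

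| f (assumed) | q | Chance of success |
|---|---|---|
| 0 | 6.1% | above 99.9% |
| 5% | 0.05795/0.99695 = 5.8% | above 99.9% |
| 10% | 0.0549/0.9939 = 5.5% | above 99.9% |
| 20% | 0.0488/0.9878 = 4.9% | above 99.9% |

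The direction is fixed: q is below p for any f above zero.

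**The case against.** The strongest reply is that the 2-day allowance is written for consent, not eligibility. Section 6.4 lists confirming eligibility before consent, and Table 2 puts it at baseline and Day 0. This stands against one tempting inference, that the protocol lets sites confirm eligibility up to 2 days after treatment; it does not say so. But Day 0 includes the hours after aspiration, and neither place says which information counts for a patient consented later.

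Three further inferences are also too strong.

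- A reader might include exclusion 3. It is limited to "Life expectancy less than 6 months due to any comorbidities", and a poor device result is not a comorbidity.
- A reader might take section 16.2 as showing that later lytic triggers exclusion 2. The definition of recurrent ischemia mentions "additional intervention such as thrombolytic therapy for threatened MI", which is not the same as lytic for the index occlusion. The wording of exclusion 2 leaves the matter open and no more.
- A reader might cite a procedural stroke. Stroke is a secondary endpoint, so removing such a patient does not by itself lower the primary rate.

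Other safeguards limit the problem. A legally authorized representative can consent, and follow-up may be by phone or outside records, so shock or ventilation alone does not make a patient unable to comply. The judgement limb is what stays open. Screen failures are logged with reasons, the SAP summarises them, and their records are open to the sponsor. That leaves a trace of the reason, but not necessarily of its timing.

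The larger values of f are demanding. Only patients who are consented late, have an early event, survive to be considered and are then screened out can contribute.

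**Conclusion.** The gap in the text is real. Exclusion 2 and the judgement limb of exclusion 4 are unanchored, late enrolment depends on meeting all criteria, and no planned analysis recovers treated patients who are screened out. Any bias runs downward.

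The documents do not show that bias will occur, and its size cannot be derived from them, because the share of patients consented late and the share screened out are not given. It matters for the pass/fail result only if the true rate is well above plan. At 16%, with 5% to 20% of event patients removed, false success rises from 1.9% to between 4.1% and 26.5%. At 6.1% the decision is unaffected and the estimate is low by about 0.3 to 1.2 percentage points. That is still relevant, since section 1.4 says the results can be used to plan later studies.

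A reader might infer false success from rates between these two, for example 14%, where the chance of passing rises from 0.15 to 0.64 at f = 20%. That rate lies inside the plan's alternative hypothesis, so passing there is not an error under the protocol's own test.

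**What to change.** 1. State in sections 5.2 and 6.4 that eligibility is judged on status and information available before the CAT RX catheter is inserted, including for patients consented afterwards. Except inclusion 4 (device use), inclusion 6 (consent) and a patient's own unwillingness to take part, because these cannot be settled before insertion for late-consented patients. Add that the investigator-judgement limb of exclusion 4 may not rest on the procedural result or later events.
2. Reconcile exclusion 2 with section 6.4 and Table 2 by stating the time period it covers. Which period applies is for the sponsor to decide.
3. On the existing screening log, record for every CAT RX-treated patient not enrolled the criterion that applied and whether its basis arose before or after insertion.
4. Report that count, and the primary rate by consent timing (before or after the procedure).

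The cost is a few lines of protocol text, one log field and one extra table. The observed rate may be slightly less favourable. The wording does not stop a site from simply not approaching a treated patient; the count in item 4 would show that only if such patients are logged.

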6.1 Overview of Study Flow

To ensure that subjects are considered for enrollment, acute coronary vessel occlusion patients referred for SOC PCI should be assessed for eligibility. All sites will keep a screen failure log of all potential study candidates who are screened and not enrolled or screened, consented, and not enrolled. Reason(s) for exclusion will be recorded. Screening information will be reported in Electronic Data Capture system (EDC).

Recruitment rates will be tracked over time for each site. The actual recruitment rates will be useful for planning further clinical studies and determining the widespread impact of the therapy.

Figure 2: Study Flow

6.2 Study Visits

Subjects enrolled in this study will follow the visit schedule below.

- 1. Baseline/Pre-Procedure
- 2. Procedure (Day 0)
- 3. Post Procedure
- 4. Discharge or 7 days, whichever occurs first
- 5. $30 \text{ days} \pm 7 \text{ days}$
- 6. $180 \text{ days} \pm 30 \text{ days}$

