6.7.6 Discharge (or 7 days, whichever occurs first)

The following information will be collected during discharge (within 1 day prior to discharge or at day 7, whichever occurs first):

- 1. Vital Signs
- 2. Laboratory assessments
- 3. 12 lead ECG
- 4. Killip Classification
- 5. CCS Classification
- 6. Cardiac concomitant medications
- 7. Events of interest/Serious Adverse Events

6.7.7 **30 Day Visit (± 7 days)**

The 30-day follow up visit may be conducted either over the phone or in person. Records within the study visit window from an outside Institution may be used to complete the visit. It is recommended that at a minimum, study patients are contacted via phone by the study site team. The following information will be collected during the 30-day follow up visit:

- 1. Subject status
- 2. NYHA Classification
- 3. Killip Classification (if visit completed in person)
- 4. CCS Classification
- 5. Cardiac concomitant medications
- 6. Events of interest/Serious Adverse Events

6.7.8 180 Day Visit (± 30 days)

The 180-day follow up may be completed over the phone or in person. Records within the study visit window from an outside Institution may be used to complete the visit. It is recommended that at a minimum, study patients are contacted via phone by the study site team. The following information will be collected during the 180-day follow up visit:

- 1. Subject Status
- 2. Vital Signs
- 3. NYHA Classification
- 4. Killip Classification (if visit is completed in person)
- 5. CCS Classification
- 6. 12 Lead ECG
- 7. Echocardiogram (if completed as SOC assessment can occur anytime between the 30 day and 180 day follow up windows)
- 8. Cardiac concomitant medications
- 9. Events of interest/Serious Adverse Events

Table 2: Schedule of Assessments

ACTIVITY	Baseline/Pre- Procedure	Procedure (Day 0)	Post-Procedure	Discharge or 7-Days (whichever occurs first)	30 days ± 7 days (Phone Call or In Person)	180 days ± 30 days (Phone Call or In Person)
Written Informed Consent	X1					
Confirm Eligibility Criteria	х	X ²				
Demographics	х					
Medical History	Х					
Vital Signs	X		X	Х		X
Laboratory Assessments	х		x	Х		
Pregnancy Test	X ³					
NYHA Classification	x				X	x
Killip Classification	x			x	Xº	Xº
CCS Classification	х			х	X	х
12 Lead ECG	х		X	Х		Х
Coronary Cineangiography		X4,5				
Echocardiogram ⁶	x		X		2	ζ ⁷
TIMI Flow Grade Score		X ⁵				
TIMI Thrombus Grade		X ⁵				
Myocardial Blush Grade		X5				
Target Lesion Characteristics		х				
Procedure		X				

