7.6.1 Adverse Events

Adverse events (AE) must be recorded by the Investigator on the CRFs and must be monitored during the study. Primary and secondary safety endpoint events, all device or procedure related events, all Serious Adverse Events (SAE), and all Unanticipated Adverse Device Effects (UADE) will be collected starting at Procedure (Day 0) through final follow-up visit. Minimum requirements of data to be recorded are: event term, event start date, seriousness, action taken, outcome and device-relatedness.

In order to ensure prompt reporting of AEs, all reportable AEs (as well as all related study data) are required to be entered into the EDC in a timely manner. Any suspected UADEs should be reported immediately by calling the Sponsor. All device related SAEs should be reported in the EDC within 72 hours of the site staff first being made aware of the occurrence of the SAE. If the EDC is unavailable, an email can be sent to Penumbra.

The Investigator must report adverse events to the IRB according to local requirements. The Investigator is responsible for adhering to reporting time frames and complying with local and federal requirements. In addition, the Investigator will report to the Sponsor and IRB any device deficiencies that could have led to a SAE, if required by federal regulations or by local authorities.

For the purpose of reporting within this protocol, pre-existing conditions or planned procedures for pre-existing conditions are not reportable as AEs unless there is worsening of the condition with an increase in severity or frequency during the course of the study.

All deaths will be reported regardless of causality. When reporting a death, the primary condition or diagnosis that contributed to the fatal outcome should be reported as a SAE, with an outcome of death. Only a single cause of death should be reported in EDC. If the cause of death is unknown, report "unknown cause of death" as a SAE.

Detailed form and narrative reports will be composed for primary and secondary safety endpoints (at a minimum).

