10.8 Statistical Analysis of Primary Endpoint

The primary endpoint is the 30-day composite endpoint. The primary effectiveness analysis will be the difference between the study group and the historical control rate of 6% observed in the TOTAL trial high thrombus burden subset.

The null hypothesis is that the difference between the composite endpoint rate and the historical control at 30 days is greater than or equal to 10%. The alternative hypothesis is the difference at 30 days is less than 10%. Formally, the null and alternative hypotheses to be tested are as follows:

H₀:
$$P_{study} - 0.06 \ge 0.10$$

H_A: $P_{study} - 0.06 < 0.10$

Where P_{study} is the proportion of patient experiencing a composite endpoint event at 30-day follow-up visit.

Statistical analysis of the primary endpoint will be conducted using a binomial comparison to test the one-sided null hypothesis that the difference in proportions is less than or equal to 0.10.

The primary safety endpoint is met if the upper limit of the 95% confidence interval of the composite primary endpoint rate is less than 16% at a one-sided alpha of 0.025. The primary analysis will be unadjusted.

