7.2 Secondary Endpoint Analysis

The secondary performance and safety endpoints (listed in Section 1) will be assessed via proportions based on the endpoint criteria and 95% confidence intervals will be presented. The Imaging Core Lab data supersede the Investigator-reported data in all analyses of imaging-based endpoints (Final TIMI Grade Flow, Final TIMI Thrombus Grade, Myocardial Blush Grade, Distal Embolization Rate). The IMR data will supersede the Investigator-reported data in all analyses of adverse events. See section 7.3 for analysis of adverse events.

Survival estimate will also be utilized for the following secondary safety endpoints to evaluate the time-to-event using Kaplan-Meier methodology: All-cause mortality within 180 days,

Cardiovascular (CV) death within 180 days, Recurrent MI within 180 days, Cardiogenic shock within 180 days, NYHA Class IV heart failure within 180 days. With the date of procedure set at day 0, any event occurring on or before day 180 will be included.

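### The final visit may fall on day 150 and ends event collection, yet the 180-day endpoints are simple proportions to day 180, so unobserved days can count as event-free

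*Combined protocol and SAP*

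**What the plan says.** - **Timing.** Protocol 6.4 times visits from the procedure: "All follow-up visits will be conducted based on date of procedure, regardless of enrollment date". Protocol 6.2 sets the final visit at "180 \text{ days} \pm 30 \text{ days". The windows in Protocol Table 2 are "30 days ± 7 days (Phone Call or In Person" and "180 days ± 30 days (Phone Call or In Person". The visits may therefore fall on days 23 to 37 and days 150 to 210.
- **How a visit is completed.** Protocol 6.7.7 and 6.7.8 allow a visit without speaking to the patient: "Records within the study visit window from an outside Institution may be used to complete the visit". A phone call by the site is recommended, not required.
- **Event collection.** Under Protocol 7.6.1, endpoint events, SAEs and device- or procedure-related events "will be collected starting at Procedure (Day 0) through final follow-up visit".
- **Subject status.** Protocol 10.5.4 and SAP 5 class a subject who completes follow-up as completed, with no requirement to reach day 180. Protocol 12.2 treats a subject as lost only if no contact is made in the last visit window.
- **180-day analysis.** SAP 7.2 gives proportions with 95% intervals for all secondary endpoints. It adds Kaplan-Meier for five named 180-day safety endpoints, without a censoring date, and does not list stent thrombosis. Its counting rule is "With the date of procedure set at day 0, any event occurring on or before day 180 will be included". Protocol 10.9 plans Kaplan-Meier more broadly, for events through 180 days.
- **Primary endpoint.** It is defined as events within 30 days, but Protocol 10.8 says the study proportion "is the proportion of patient experiencing a composite endpoint event at 30-day follow-up" and ties this to the visit. SAP 7.1 refers to a 30-day timepoint. SAP 10 gives sensitivity analyses for a missing 30-day outcome and does not define when the outcome is missing.

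**The concern.** The plan says which events count up to day 180. It does not say how long a subject must be observed to count as event-free. A subject whose final visit is on day 150 has no later contact, is classed as completed, and belongs to the ITT sample. In a simple proportion that subject adds one to the denominator and nothing to the numerator, whatever happens on days 151 to 180. The 180-day mortality, recurrent MI, shock, heart failure and stent thrombosis rates are then understated. These are safety and performance rates that the study exists to report, and readers will compare them with 180-day rates from other studies.

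A weaker form of the same gap touches the primary endpoint. A subject seen before day 30 and never contacted again might be treated as observed and event-free, and so stay out of the SAP 10 worst-case analysis.

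**Working it through.** **The plan's own figures.** SAP 2 gives 360 subjects, an assumed rate of 6.1% and 99% power against a 16% limit at one-sided 0.025. With an exact (Clopper-Pearson) limit, success requires at most 43 events in 360. Power at 6.1% is above 0.9999, so the stated 99% is met, and 360 / (1 − 0.10) = 400. None of this changes below.

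**Windows.** 30 − 7 = day 23, leaving 7 of 30 days (23%) uncovered by that visit. 180 − 30 = day 150, leaving 30 of 180 days (17%).

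**180-day endpoints, share of late events missed.** Assume events after day 30 are spread evenly over days 30 to 180 (150 days). For a last contact on day c, the unobserved time is max(0, 180 − c).

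- Final contacts uniform over days 150 to 210: the mean is (30 × 30 / 2) / 60 = 7.5 days, and 7.5 / 150 = 5%.
- All final contacts on day 150: 30 / 150 = 20%.
- The documents give no late event rate. Assuming 1% to 3% in 360 subjects (3.6 to 10.8 events), the loss is 0.18 to 0.54 events per endpoint at 5%, and 0.72 to 2.16 at 20%.

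**180-day endpoints, effect on the rate.** With every final contact on day 150 and a constant hazard from day 0, the rate seen is 1 − (1 − p)^(150/180).

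| True 180-day rate | Seen | Understated by | Events per 400 |
|---|---|---|---|
| 3% | 2.51% | 0.5 points | 2.0 |
| 5% | 4.18% | 0.8 points | 3.3 |
| 7% | 5.87% | 1.1 points | 4.5 |
| 10% | 8.41% | 1.6 points | 6.4 |

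A constant hazard probably overstates the loss. If risk is concentrated early, for example 6.1% by day 30 and 7.0% by day 180, the loss is about 0.2 points, or 0.7 events per 400.

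**Primary endpoint.** Event collection runs to the final visit, so a contact on days 150 to 210 also covers days 23 to 30. The gap is confined to subjects seen on days 23 to 29 with no later contact. Take 10% of subjects, the full planned attrition, all last seen on day 23, and a constant hazard:

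- Rate seen in that group: 1 − (1 − 0.061)^(23/30) = 4.71%.
- Overall: 0.9 × 6.1% + 0.1 × 4.71% = 5.96%.
- Events missed: 36 × (0.061 − 0.0471) = 0.5, against about 22 expected and 43 allowed.
- Chance of false success at a true rate of 16%: from 0.0185 to 0.028 (0.023 if the group is 5%).

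**The case against.** - **Kaplan-Meier is already planned.** For the five listed safety endpoints an estimate that handles early last contact exists, and Protocol 10.9 could be read to cover stent thrombosis. This stands, and it makes the fix cheap. But SAP 7.2 puts Kaplan-Meier beside the proportions without saying which is the headline, gives no censoring date, and leaves stent thrombosis off its list.
- **Counting as event-free is inferred from silence.** True: no passage states that rule. It is, however, what results when a simple proportion is taken over all enrolled subjects and nothing removes or censors an early completer.
- **The effect is small.** Also true. The 20% figure needs every final visit on day 150, and the 180-day endpoints carry no hypothesis.
- **The primary result is at risk.** A reader might infer this from the day-23 opening. If every subject were seen on day 23 and never again, 6.1% would appear as 4.7%, and false success at a true 16% would reach 0.41. The documents do not support that scenario, because Protocol 7.6.1 and Table 2 collect events through the 180-day visit.
- **The error always favours the device.** A reader might infer this too. It does not hold for the primary endpoint: if Protocol 10.8 is read literally, a visit on days 31 to 37 could bring in events after day 30 and raise the rate.

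**Conclusion.** The point holds for the 180-day endpoints. Followed as written, the plan understates the simple proportions by about 5% of late events if final contacts are uniform over the window, and by up to 20% if all are on day 150. Both figures assume late events spread evenly over days 30 to 180. In absolute terms this is about 0.2 to 1.6 percentage points in the extreme where every final visit is on day 150, depending on the true rate and on how early the risk falls. Stent thrombosis is the most exposed, because SAP 7.2 gives it no Kaplan-Meier estimate. No success criterion is affected.

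For the primary endpoint the gap is narrow. Even with 10% of subjects last seen on day 23, the rate moves only from 6.1% to about 5.96%, and the conclusion at the planned rate is not threatened. What remains there is a wording mismatch and an undefined minimum observation time. Symmetric visit windows are not in themselves an error.

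**What to change.** 1. **SAP 7.2.** Make the Kaplan-Meier estimate at day 180 the headline for the 180-day endpoints and add stent thrombosis. State that subjects are censored at last contact, or at the date of the outside record that completed the visit. Report the number at risk at day 180: if nearly all final contacts came before then, the curve would only carry an earlier estimate forward.
2. **SAP 7.1 and Protocol 10.8.** Count primary events dated day 0 to 30, in the same words in both. Class a subject as observed only with an event by day 30 or any contact on or after day 30, including the 180-day visit. Send all others to the SAP 10 sensitivity analyses. The same rule can serve stroke and major bleeding within 30 days.
3. **Optional.** Schedule contacts, and date outside records, on or after day 30 and day 180. Visits may be by phone, so the burden is light. But a final window of days 180 to 210 is half the present one, and subjects reachable only on days 150 to 179 could become lost to follow-up under Protocol 12.2.

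Items 1 and 2 cost only wording, and the SAP needs approval only before database lock. Reported 180-day rates would be slightly higher and their intervals slightly wider. Sample size and power do not change.
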